11.3.2 Pregnancy

All women who participate in the study must be postmenopausal or surgically sterile. Women should be instructed to contact the investigator or study staff immediately if pregnancy occurs or is suspected.

Pregnancy testing will be conducted prior to administration of the IP on every woman who is not surgically sterile. A woman who is found to be pregnant at the screening visit will be excluded from the study and considered to be a screening failure.

Men who are biologically capable of having children must agree and commit to use an adequate form of contraception (see Appendix B) for the duration of the treatment period and for 3 months after the last administration of study drug. A male subject is considered capable of having children even if his sexual partner is sterile or using contraceptives.

A woman who becomes pregnant during IP treatment or within 30 days of discontinuing the IP will be immediately discontinued from study participation. The investigator must report the pregnancy as if it were an SAE within 24 hours of learning of the pregnancy, to MMS Pharmacovigilance using the Pregnancy Notification and Outcome Form via the same fax number and/or email address as for SAE reporting.

Early Termination Visit assessments are required as soon as possible after learning of the pregnancy. The investigator is also responsible for following the pregnancy until delivery or termination. The follow-up information must be reported to MMS Pharmacovigilance using a new Pregnancy Notification and Outcome Form. The event meets the SAE criterion only if it results in a spontaneous abortion or a congenital anomaly.

11.3.3 Overdose

13-Apr-2022

The maximal dose of IP should not be exceeded during the study. The investigator must report any overdose to MMS PV within 24 hours of learning of the overdose using the Overdose Report Form provided by MMS PV. In case of known or suspected overdose, symptomatic treatment as well as monitoring of vital functions should be performed based on the judgment of the investigator. If the overdose does not result in an AE, it should be reported in written form to the designated individuals who receive SAE notification. The information contained therein should include study

site identification, reporter identification, subject identification, IP, dose, action taken (eg, supportive measures or therapy), and any comments.

12 DATA SAFETY MONITORING BOARD

A data safety monitoring board will not be used in this study.

13 STATISTICS

13.1 Statistical Analysis

This section presents a summary of the planned statistical analyses. A statistical analysis plan (SAP) that describes the details of the analyses to be conducted will be finalized prior to database lock for the interim analysis.

Unless otherwise indicated, all formal testing of statistical significance will be one-sided, and a difference resulting in a 1-sided P value of \leq 0.025 will be considered statistically significant. For estimation purposes, 2-sided 90% and 95% confidence intervals will be presented.

Summary statistics will be provided for the variables described below. For continuous variables, these statistics will typically include the number of subjects, mean, standard deviation (SD), median, minimum, and maximum. For categorical variables, these statistics will typically include the number and percentage of subjects in each category.

13.1.1 Analysis Populations

The following 4 analysis populations are planned for this study:

- Screening: all subjects who provide informed consent and/or assent and provide demographic and/or baseline screening assessments, regardless of the subject's randomisation and treatment status in the study.
- Safety: The safety population will include all subjects who receive at least 1 dose of double-blind study medication.
- Modified intent-to-treat (mITT): The modified intent-to-treat population will be used for all efficacy analyses and will include all randomised subjects who receive at least 1 dose of double-blind study medication and have at least 1 post-baseline NRS assessment.
- PK: The PK population will include all subjects for whom a PK sample was obtained and analysed.

Inclusion in the analysis populations will be determined prior to database lock.

If a subject is randomised incorrectly or is administered the incorrect IP, analyses of the mITT population will be based on the IWRS-assigned treatment whereas all other analyses will be based on the actual treatment.

13.1.2 Study Subjects and Demographics

13.1.2.1 Disposition and Withdrawals

The numbers of subjects randomised, completing, and withdrawing, along with reasons for withdrawal, will be tabulated overall and by treatment group. The number of subjects in each analysis population will be reported.

13.1.2.2 Protocol Deviations

Subjects who violate any inclusion and/or exclusion criteria or who have major protocol deviations during the study (such as incorrect treatment assignment or use of prohibited medications) will be summarised and listed.

Page 78 of 114

13.1.2.3 Demographics and Other Baseline Characteristics

These analyses will be conducted for all analysis populations.

Demographic variables will be collected for any eventual analysis of differences in response to the IP, in accordance with local regulatory requirements. Baseline subject characteristics including medical history, physical and neurological examination findings, and other baseline disease history will be listed and included in summaries as appropriate.

Prior and concomitant medications will be summarized by treatment group, by the number and percentage of subjects taking each medication, classified using World Health Organization Drug Dictionary Anatomical Therapeutic Chemical classes and preferred terms (PTs).

13.1.3 Exposure and Compliance

Investigational product administration will be summarized in terms of each subject's total dose and number of infusions received. Descriptive statistics for these quantities, including the mean, median, SD, minimum, maximum, and quartiles, will be provided by treatment group. In addition, any incomplete infusions will be listed.

13.1.4 Efficacy Analysis

All efficacy variables will be summarized descriptively including number of observations, mean, SD, minimum, median, and maximum for continuous variables, and frequency of observations in each category and percentage for categorical variables.

Primary and secondary endpoint efficacy data will be tabulated according to the 'Observed Cases' approach. In addition, if there is missing data at a key analysis time-point (Weeks 4, 8, and 12) then results will also be tabulated according to 'Last-Observation-Carried-Forward' (LOCF) and 'Baseline-Observation-Carried-Forward' (BOCF). For example, if an endpoint is missing from a post-randomisation visit then the last non-missing post-baseline endpoint recorded prior to the visit will replace the missing value. For endpoints with separate scales, if an individual scale item is missing then the item will be carried forward from the previous visits rather than the total score. For post-baseline diary data, if a subject has at least 4 out of 7 days' diary data prior to the visit, then this will be taken as a valid observed weekly average score. However, if a subject has 3 or fewer days of diary data, this will be counted as a missing weekly score, and the LOCF approach will carry forward the last 7 non-missing entries of the diary data prior to the visit in order to calculate the weekly mean score at endpoint score.

The main statistical analysis of the primary efficacy endpoint at Week 12 will use the multiple comparison procedure modelling (MCP-Mod) approach on LOCF data, which is a well-established statistical methodology for establishing both the existence of a dose response and modelling the underlying dose-response relationship. Both EMA (2014)⁴⁴ and FDA (2015)⁴⁵ have recognized MCP-Mod as an efficient statistical methodology for model-based design and analysis of Phase 2 dose finding studies under model uncertainty.

There are two steps to MCP-Mod:

13-Apr-2022

- 1. The 'MCP' step is a rigorous method to establish presence of a dose response while protecting the type I error and, if the dose-response relationship is statistically significant, then
- 2. The 'MOD' step estimates the dose response function and associated model parameters, such as ED50 (the effective dose for 50% of the population) in the case of E_{max} relationship.

The MCP test will use linear contrasts corresponding to the five candidate models described in Section 13.2. The underlying model will be an analysis of covariance (ANCOVA) with dependent variable 'change from baseline to Week 12', and independent variables will include dose, 'baseline score' and co-medication type. The random error is assumed to be normally and independently distributed with constant variance.

If the MCP test is statistically significant, then the MOD step will select the most appropriate model from hyperbolic E_{max}, sigmoidal E_{max}, or linear using the 'E_{maxlin}' approach as described by Kirby et al. (2011).⁴⁶ From this model (including the same covariates as the ANCOVA model), various estimates will be derived (together with confidence intervals) of parameters of interest such as ED50, ED90, dose to achieve selected target effects, and model estimates of the treatment effect at doses studied.

In addition to the analysis of all stages combined, a supplementary analysis using an adaptive MCP-MOD method will be conducted where stages 2+3 and stage 4 will be analysed separately and the results combined using an inverse-normal p-value combination function, with weights related to the original planned sample sizes. Further details of the analysis will be included in the SAP.

To complement the MCP-MOD outputs, estimates and confidence intervals of each pairwise comparison versus placebo from the ANCOVA model described in the MCP step will be produced.

In addition, changes from baseline in continuous endpoints will be compared between treatment groups using mixed models repeated measures including terms for pooled site, treatment (as a factor), time point (as a factor), the interaction between treatment and time point, and the baseline value of the variable undergoing analysis. Binary outcomes will be analysed using generalized estimating equations, with the models including the same terms as the mixed models repeated measures. Other non-binary categorical endpoints will be analysed using Cochran-Mantel-Haenszel statistics. These analyses will be conducted on observed cases. Further details of the longitudinal modelling will be included in the SAP.

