PK: Noncompartmental analysis methods will be used. The PK parameters will be summarized by MEDI7352 dose using descriptive statistics.

CCI

CC

Safety Analyses: Safety and tolerability data will be summarised descriptively, including tables, listings, and graphs, as appropriate.

SAMPLE SIZE DETERMINATION

There is no formal sample size calculation for stage 1; 10 subjects in stage 1 is considered sufficient for the initial assessment of safety. The sample size for stages 2-4 combined was determined by a formal power calculation (see below) and the size of stage 3 was defined to confirm decision making for the stage 4 sample size and dose allocation ratio.

This study is powered at greater than 80% to detect a statistically significant (1-sided alpha = 0.025) dose-response relationship when the true Week 12 placebo-corrected change from baseline difference at the is 1.25 on the 11-point NRS scale (MEDI7352-placebo treatment) and the true dose-response follows a hyperbolic E_{max} relationship, with the effective dose for 50% of the population (ED50) within the range This calculation also assumes:

- The true SD is 2.4, which is based on other studies undertaken with pregabalin in PDN
- The data from stages 2, 3 and 4 are combined so that the number of subjects evaluable for the dose response analysis is 236. The total number of subjects evaluable for efficacy for the placebo, CCI and doses is equal to 81, 37, 51 and 67, respectively.

Confidential

The dose-response hypothesis test is multiplicity adjusted in order to control the type 1-error.

The above calculations were performed using the following parameters:

- Population SD (of change from baseline to week 12) = 2.4
- Placebo effect = 1-point reduction in NRS and 450 µg effect = 2.25 reduction from baseline, ie, delta = 1.25
- Linear contrasts were determined from 5 'candidate dose' response models which are all E_{max} models with decreasing potency/increasing ED50: 7.5, 15, 30, 60, 750 μg/kg. The 5th case is essentially linear in dose.
- Power was assessed across 16 alternative true dose response curves, 12 E_{max} with ED50 ranging from 0.375 to 750 µg/kg, 3 logistic and 1 quadratic, all having a Week 12 placebo-corrected change from baseline difference at the of 1.25.

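### The MMRM as listed has one baseline slope and no co-medication term, so its covariates differ from those of the primary ANCOVA: a small precision loss and a less clean comparison with the LOCF result

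*Protocol*

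**What the plan says.** Protocol section 13.1.4 (Efficacy Analysis) describes two models that both apply to the change in weekly average pain at Week 12.

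- **Primary analysis.** It "will use the multiple comparison procedure modelling (MCP-Mod) approach on LOCF data". In the underlying ANCOVA, "independent variables will include dose, 'baseline score' and co-medication type". The MOD step keeps these covariates, and the pairwise estimates against placebo come from the same ANCOVA. No site term is listed.
- **Longitudinal analysis.** Changes in continuous endpoints are also compared with "mixed models repeated measures including terms for pooled site, treatment (as a factor), time point (as a factor), the interaction between treatment and time point". The list closes with "the interaction between treatment and time point, and the baseline value of the variable undergoing analysis". The GEE models for binary endpoints take the same terms. For the data used, the section says "These analyses will be conducted on observed cases", and it adds "Further details of the longitudinal modelling will be included in the SAP".

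The synopsis (section 2.1) repeats the MMRM terms. Section 9.5 states that randomisation is neither stratified nor blocked by centre, so neither co-medication nor site is a design factor.

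**The concern.** A single baseline coefficient assumes that baseline pain has the same relation to change at every visit. If that relation differs between Week 2 and Week 12, the common slope is not the Week 12 slope, and some baseline variation stays in the Week 12 comparison. Co-medication type is in the primary model and is already collected, yet it is absent from the MMRM.

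The two covariate sets differ in both directions: co-medication appears only in the ANCOVA and pooled site only in the MMRM. For the continuous Week 12 pain change, the MMRM is the only model that the protocol explicitly places on observed cases, so readers will set it beside the LOCF result. If the two disagree, the covariates as well as the handling of missing data could be the cause. What is at stake is a little precision and ease of interpretation, not the validity of the primary test.

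**Working it through.** **1. The plan's own figure.** The synopsis states "This study is powered at greater than 80% to detect a statistically significant (1-sided alpha = 0.025) dose-response relationship", with an SD of 2.4, "effect = 2.25 reduction from baseline, ie, delta = 1.25", and 81, 37, 51 and 67 evaluable subjects. The other doses are redacted, so four dose sets with a top dose of 450 were assumed. Simulating the multiplicity-adjusted contrast test then gives 88–95% power over E_max curves with ED50 from 0.375 to 750. As a simple cross-check on 81 against 67 subjects:

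- SE = 2.4 × √(1/81 + 1/67) = 0.396
- 1.25 / 0.396 = 3.15
- power = Φ(3.15 − 1.96) = 88.4%

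The stated lower bound is met, and the MMRM plays no part in it. The logistic and quadratic true curves were not rerun.

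**2. Omitting co-medication.** The SE is inflated by 1/√(1 − R²). The protocol gives no R², so a range is shown.

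| R² (assumed) | SE ratio | Pairwise power with adjustment |
|---|---|---|
| 0 | 1.000 | 88.4% |
| 0.01 | 1.005 | 88.7% |
| 0.02 | 1.010 | 89.0% |
| 0.05 | 1.026 | 89.9% |
| 0.10 | 1.054 | 91.4% |

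**3. One common baseline slope.** With complete data, the fitted common slope is the covariance-weighted average of the visit slopes, 1′R⁻¹b / 1′R⁻¹1. The Week 12 SE ratio is about √(1 + (gap × SD_baseline)² / σ²), where the gap is the Week 12 slope minus the common slope. Assumptions:

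- baseline SD 1.4
- Week 12 residual SD σ = 2.2
- six visits, with residual SD rising from 70% to 100% of 2.2 and correlation 0.85 between adjacent visits

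The visit weights are then about 0.72, 0.03, 0.03, 0.03, 0.03 and 0.16. For slopes running linearly from −0.1 to −0.6, the common slope is −0.208 and the gap is 0.392 in size. The ratio is √(1 + (0.392 × 1.4)² / 2.2²) = √(1 + 0.301/4.84) = 1.031. The same formula gives 1.005 for −0.2 to −0.4 and 1.077 for 0 to −0.8. It gives exactly 1 for a constant slope.

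**4. Simulated MMRM with dropout.** This used the same assumptions, an unstructured covariance, dropout depending on the last observed pain, and 200 trials per row. Pooled site was not modelled. The figures are mean model SEs for top dose against placebo at Week 12.

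| Slope, first to last visit | Co-medication R² | Dropout setting | SE as listed | SE with both terms | Fall |
|---|---|---|---|---|---|
| constant −0.4 | 0 | 10% | 0.383 | 0.383 | 0 |
| −0.2 to −0.4 | 0 | 10% | 0.382 | 0.380 | 0.5% |
| −0.2 to −0.4 | 1.1% | 10% | 0.385 | 0.381 | 1.0% |
| −0.2 to −0.4 | 4.3% | 10% | 0.395 | 0.384 | 2.8% |
| −0.1 to −0.6 | 0 | 10% | 0.393 | 0.382 | 2.8% |
| 0 to −0.8 (extreme) | 0 | 10% | 0.410 | 0.382 | 6.8% |
| −0.1 to −0.6 | 1.1% | 25% | 0.429 | 0.414 | 3.5% |

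The synopsis anticipates about 10% withdrawal. In every row, adding both terms moved the mean estimate by less than 0.01 NRS points. In the 25% row the MMRM gave −1.278 as listed and −1.282 with both terms, against −1.194 for the LOCF ANCOVA; the true value was −1.25.

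**The case against.** The strongest reply is that nothing has been fixed wrongly. The list of MMRM terms is open, the paragraph leaves longitudinal detail to the SAP, and extra covariates are ordinary SAP content. The MMRM is an additional analysis of continuous endpoints in general. The protocol neither calls it a sensitivity analysis of the LOCF result nor rests the primary conclusion on it. The slopes, baseline SD and R² used above are not in the document, which also makes no claim that co-medication is prognostic.

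Most of this stands, and it sets the limits of the point. What remains is that the protocol does write out a model, names one interaction with time but not the other, and gives the two models different covariates a few sentences apart. An SAP that follows the list inherits the mismatch.

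A reader might infer three stronger claims, which the documents do not support.

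- **The protocol forces a common slope.** It does not: the wording leaves room for more terms.
- **The MMRM is a poor check on LOCF.** In the simulations its mean estimate hardly changed with the extra terms, and the contrast with LOCF remained.
- **The common slope biases the Week 12 estimate.** In the −0.1 to −0.6 case, a one-SE chance imbalance in baseline shifts a single trial's estimate by 0.392 × 1.4 × √(1/81 + 1/67) = 0.09 points. Over randomisations this averages to zero. It is also the variance already counted: √(0.363² + 0.091²) / 0.363 = 1.031, the ratio found in step 3. It must not be added as a separate harm.

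Nor is the MMRM the only model-based observed-case analysis of Week 12 pain of any kind, because the 30% and 50% responder endpoints go into GEE models.

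**Conclusion.** The point holds as a minor improvement. As listed, the MMRM has one baseline main effect and no co-medication term, and its covariates differ from the primary ANCOVA's in both directions. The Week 12 precision loss is about 0–3% of the SE for moderate assumed slopes, a co-medication R² of 1–5% and the anticipated 10% withdrawal. It is slightly more (3.5%) in the one run at 25% dropout and about 7% only for an extreme slope change. It is nil if the slope is constant and co-medication is not prognostic. These sizes rest on assumed slopes, baseline SD, covariance and R², and no precision gain was calculated for the GEE models.

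The second consequence does not depend on those values: an MMRM-versus-LOCF comparison of Week 12 pain mixes covariate differences with missing-data handling. The primary test and the stated power are unaffected.

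**What to change.** In section 13.1.4 and the synopsis, or in the SAP's longitudinal model:

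- Add baseline-by-time point and co-medication type to the MMRM for the continuous endpoints.
- Add co-medication type to the GEE models. Include baseline-by-time point there only where a baseline value exists. PGIC has none in the Schedule of Events (Table 2-1), so the term cannot be fitted for it.
- For Week 12 pain, either give the MMRM and the ANCOVA the same pooled-site term or state why they differ. Without this step, the first change alone would not align the two covariate sets.

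Baseline pain and concomitant medication are already collected. The cost is a few degrees of freedom and a sentence or two of text.

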13.1.4.1 Efficacy Endpoints

13-Apr-2022

The primary efficacy endpoint is the change in the weekly average of the average daily pain scores from the baseline week to Week 12, as measured on an 11-point (0-10) NRS.

The secondary endpoints are the following:

- Change in the weekly average of the average daily pain score, as measured on an 11-point (0-10) NRS, from baseline to Weeks 2, 4, 6, 8, and 10 of treatment and the week before the follow-up visit.
- Percentage of subjects who have achieved ≥30% and ≥50% reductions in the weekly average of the average daily pain score from baseline during Weeks 4, 8, and 12 of treatment and the week before follow-up.
- Change in Galer NPS from baseline to Days 28, 56, and 84 of treatment and the follow-up visit.
- Change in DSIS from baseline to Days 28, 56, and 84 of treatment and the follow-up visit.

- Proportion of subjects who have 'improved', 'much improved', or 'very much improved' relative to baseline on the PGIC on Days 28, 56, and 84 of treatment and the follow-up visit.
- Change in the SF-36 from baseline to Day 84 of treatment.
- Usage of rescue medication (yes/no) from baseline to Week 12 of treatment.

13.1.5 Clinical Pharmacology Analyses

13.1.5.1 Pharmacokinetics

For noncompartmental analysis, plasma concentrations will be listed and summarized at each time point using descriptive statistics; graphical representations will also be provided. The PK parameters will be summarized by dose using descriptive statistics including geometric mean, geometric SD, arithmetic coefficients of variation, and geometric coefficients of variation. The potential relationships between PK and efficacy and safety parameters may be explored graphically. Statistical analyses of PK parameters will be outlined in the SAP. Subjects receiving placebo will not be included in the summary and analysis of PK parameters.

13.1.5.2 Pharmacodynamics

The PD variables (free and/or total NGF) will be summarized using descriptive statistics. The association between PD variables and efficacy endpoints will be explored. Further details will be included in the SAP.

13.1.5.5 Immunogenicity

Immunogenicity results will be listed and the effects of ADAs on PK and PD will be explored.

13.1.6 Safety and Tolerability Analyses

Safety and tolerability data will be summarised descriptively, including tables, listings, and graphs, as appropriate. Unless otherwise stated, descriptive summary statistics for continuous variables will include number of observations, mean (ie, arithmetic mean), SD, minimum, median, and

maximum. Descriptive summary statistics for categorical data will include frequencies and percentages.

